Arm Description	Single oral dose of nirmatrelvir/ ritonavir [REDACTED] CCI [REDACTED] [REDACTED] commercial tablets under fasted conditions	Single oral dose of nirmatrelvir/ ritonavir [REDACTED] CCI [REDACTED] [REDACTED] oral powder mixed with water under fasted conditions	Single oral dose of nirmatrelvir/ ritonavir [REDACTED] CCI [REDACTED] [REDACTED] oral powder mixed with infant formula under fasted conditions	Single oral dose of nirmatrelvir/ ritonavir [REDACTED] CCI [REDACTED] [REDACTED] oral powder mixed with vanilla pudding under fasted conditions	Single oral dose of nirmatrelvir/ ritonavir [REDACTED] CCI [REDACTED] [REDACTED] oral powder mixed with vanilla pudding under fed conditions

Statistical Methods:

Natural log transformed AUC_{inf} (if data permits), AUC_{last} and C_{max} will be analyzed using a mixed effect model with sequence, period and treatment as fixed effects and participant within a sequence as a random effect.

Ethical Considerations:

Nirmatrelvir is not expected to provide any clinical benefit to healthy participants in this study. This study is designed primarily to further the understanding of human PK of nirmatrelvir.

Based on data from Study C4671001, C4671019, C4671024, C4671005 and C4671006, the clinical safety profile of nirmatrelvir appears to be acceptable at single doses up to 1500 mg alone and up to 2250 mg administered with ritonavir (100 mg at -12h, 0h, 12h), split dosing administration (3 doses of 750 mg) at short intervals (approximately 2 hours from the previous dose), and at repeated daily doses administered orally for 10 days of up to 500 mg nirmatrelvir q12h with 100 mg ritonavir q12h.

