4. STUDY DESIGN

4.1. Overall Design

This is a Phase 1, open-label, single dose, randomized, crossover study in healthy adult participants to estimate rBA of nirmatrelvir/ritonavir **CCI** [REDACTED] oral powder mixed with 3 different food vehicles (Test formulations) compared to the nirmatrelvir/ritonavir **CCI** [REDACTED] commercial tablets (Reference formulation) under fasted conditions, and to estimate the effect of food on the rBA of the nirmatrelvir/ritonavir oral powder formulation mixed with vanilla pudding. The study will also assess the safety, tolerability, and palatability of nirmatrelvir/ritonavir in healthy adult participants.

Approximately 12 adult healthy male and/or female participants will be enrolled and randomized to 1 of 6 possible treatment sequences. Participants who discontinue from the study for non safety reasons may be replaced at the sponsor's discretion in collaboration with the investigator. The replacement participant will receive the same treatment sequences as the participant who discontinued.

Each enrolled participant will participate in 5 study periods to receive 5 different treatments according to the sequence determined by randomization:

- Treatment A: Single oral dose of nirmatrelvir/ritonavir **CCI** [REDACTED] tablets under fasted condition
- Treatment B: Single oral dose of nirmatrelvir/ritonavir **CCI** [REDACTED] oral powder mixed in water under fasted condition
- Treatment C: Single oral dose of nirmatrelvir/ritonavir **CCI** [REDACTED] oral powder mixed in infant formula under fasted condition
- Treatment D: Single oral dose of nirmatrelvir/ritonavir **CCI** [REDACTED] oral powder mixed in vanilla pudding under fasted condition

- Treatment E: Single oral dose of nirmatrelvir/ritonavir **CCI** oral powder mixed in vanilla pudding under fed condition

Participants will be randomly assigned to 1 of 6 sequences as shown below in Table 3. Participants will be discharged on Day 4 of Period 5, following completion of all assessments. Between each treatment, a minimum of 4 days washout is proposed to minimize any residual nirmatrelvir concentrations prior to start of the next treatment. The total planned duration of participation from the Screening visit to the last follow-up phone call, is approximately 12 weeks.

Table 3. Randomized Treatment Sequences

Treatment Sequence	Period 1	Period 2	Period 3	Period 4	Period 5
Sequence 1 (N = 2)	Treatment A	Treatment B	Treatment C	Treatment D	Treatment E

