9.3.2. Statistical Methods for PK Data

For the primary objective, natural log transformed AUC_{inf} (if data permits), AUC_{last} and C_{max} will be analyzed using a mixed effect model with sequence, period and treatment as fixed effects and participant within a sequence as a random effect. Estimates of the adjusted mean differences (Test-Reference) and corresponding 90% confidence intervals will be obtained from the model. The adjusted mean differences and 90% confidence intervals for the differences will be exponentiated to provide estimates of the ratio of adjusted geometric means (Test/Reference) and 90% confidence intervals for the ratios. For primary objective, Treatment A will be the Reference treatment while Treatments B, C, D and E will be the Test treatments. For food effect estimation (periods 4 and 5 only) Treatment D will be the Reference treatment while Treatments E will be the Test treatment.

PK parameters, including plasma AUC_{inf} (if data permits), AUC_{last} , C_{max} , **CCI** [REDACTED] of nirmatrelvir and ritonavir will be summarized descriptively by treatment. For AUC_{inf} (if data permits), AUC_{last} , and C_{max} , a listing of the individual participant ratios (Test/Reference) will be provided. Box and whisker plots for AUC_{inf} (if data permits), AUC_{last} , and C_{max} , will be plotted by treatment.

The plasma concentrations of nirmatrelvir and ritonavir will be listed and descriptively summarized by nominal PK sampling time and treatment. Individual participant, as well as mean and median profiles of the plasma concentration time data will be plotted by treatment using actual (for individual) and nominal (for mean and median) times respectively. Mean and median profiles will be presented on both linear and semi-log scales.

Additional specifications about the tables, listings, and figures will be outlined in the SAP.

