6. ANALYSES AND SUMMARIES

6.1. Primary Endpoints

For the estimation of rBA of nirmatrelvir/ritonavir oral powder in 3 different food delivery vehicles relative to the nirmatrelvir/ritonavir commercial tablets, *natural log transformed AUC_{inf} (if data permits), AUC_{last} and C_{max} will be analyzed using a mixed effect model with sequence, period and treatment as fixed effects and participant within a sequence as a random effect. Estimates of the adjusted mean differences (Test-Reference) and corresponding 90% confidence intervals will be obtained from the model. The adjusted mean differences and 90% confidence intervals for the differences will be exponentiated to provide estimates of the ratio of adjusted geometric means (Test/Reference) and 90% confidence intervals for the ratios. Treatment A will be the Reference treatment while Treatments B, C, D and E will be the Test treatments.*

Residuals from the models will be examined for normality and the presence of outliers via visual inspection of plots of residuals vs predicted values and normal probability plots of residuals but these will not be included in the CSR. If there are major deviations from normality or outliers then the effect of these on the conclusions will be investigated through alternative transformations and/or analyses excluding outliers. Justification for any alternative to the planned analysis will be given in the report of the study.

[figure not shown]

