Appendix 1. SAS Code for Analyses

An example of the PROC MIXED code is provided below:

For primary objectives:

```
proc mixed data=tab.pk;
  class seq period trt participant;
  model l&var=seq period trt/ ddfm=KR;
  random participant(seq) /subject=participant(seq);
  lsmeans trt;
  estimate 'B vs A' trt -1 1 0 0 0 /cl alpha=0.1;
  estimate 'C vs A' trt -1 0 1 0 0 /cl alpha=0.1;
  estimate 'D vs A' trt -1 0 0 1 0 /cl alpha=0.1;
  estimate 'E vs A' trt -1 0 0 0 1 /cl alpha=0.1;

  ods 'Estimates' out=est&var;
  ods 'lsmeans' out=ls&var;
  ods 'covparms' out=cov&var;
  ods 'tests3' out=tst&var;
run;
```

/* Letter assignments for treatments (trt) within the estimate statement above are as follows

A: Single oral dose of nirmatrelvir/ritonavir CCI [REDACTED] tablets under fasted condition (Reference);

B: Single oral dose of nirmatrelvir/ritonavir CCI [REDACTED] oral powder mixed in water under fasted condition (Test);

C: Single oral dose of nirmatrelvir/ritonavir CCI [REDACTED] oral powder mixed in infant formula under fasted condition (Test);

D: Single oral dose of nirmatrelvir/ritonavir CCI [REDACTED] oral powder mixed in vanilla pudding under fasted condition (Test);

E: Single oral dose of nirmatrelvir/ritonavir CCI [REDACTED] oral powder mixed in vanilla pudding under fed condition (Test) */

For secondary objective:

```
proc mixed data=tab.pk;
  where trt in ("D", "E");
  class seq period trt participant;
  model l&var= seq period trt / ddfm=KR;
  random participant(seq) / subject=participant(seq);
  lsmeans trt;
  estimate 'E vs D' trt -1 1 /cl alpha=0.1;
```

```
ods 'Estimates' out=est&var;
ods 'lsmeans' out=ls&var;
ods 'covparms' out=cov&var;
ods 'tests3' out=tst&var;
run;
```

/* Letter assignments for treatments (trt) within the estimate statement above are as follows;
D: Single oral dose of nirmatrelvir/ritonavir **CCI** [REDACTED] oral powder mixed in vanilla
pudding under fasted condition (Reference);
E: Single oral dose of nirmatrelvir/ritonavir **CCI** [REDACTED] oral powder mixed in vanilla
pudding under fed condition (Test) */

CCI [REDACTED]

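### The planned model cannot estimate two of the four primary contrasts (D vs A and E vs A), because treatment block and period block coincide in every sequence

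*SAP*

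**What the plan says.** Protocol 9.3.2 and SAP 6.1 specify one model for the four primary comparisons, a "mixed effect model with sequence, period and treatment as fixed effects and participant within a sequence as a random effect". The protocol synopsis repeats it. On the comparisons, Protocol 9.3.2 states: "For primary objective, Treatment A will be the Reference treatment while Treatments B, C, D and E will be the Test treatments".

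The SAP Appendix 1 code for the primary objectives has "class seq period trt participant", so period enters as a five-level factor. It uses all five periods and requests "estimate 'D vs A' trt -1 0 0 1 0 /cl alpha=0.1" and "estimate 'E vs A' trt -1 0 0 0 1 /cl alpha=0.1", along with B vs A, C vs A and the treatment LS means.

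The sequences come from Protocol 4.1: "Participants will be randomly assigned to 1 of 6 sequences as shown below in Table 3". They are ABCDE, BCADE, CABDE, ACBED, BACED and CBAED, with two participants each. Protocol 9.3.2 itself recognises where D and E fall: "For food effect estimation (periods 4 and 5 only) Treatment D will be the Reference treatment".

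SAP 2.1 records no change from the protocol analysis. Protocol 4.2 gives control of period effects as the reason for the crossover.

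**The concern.** No sequence places A, B or C after Period 3, or D or E before Period 4. A model that lets every period have its own level cannot tell the effect of pudding (fasted or fed) from whatever distinguishes Periods 4–5 from Periods 1–3. This is exact aliasing, not low precision.

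At stake are two of the four primary objectives: pudding fasted against tablets and pudding fed against tablets. As written, they would be left with individual ratios and descriptive summaries by treatment. The failure would show when the code is run, but SAP 5 places final analysis after data release and SAP 7 allows open-label data reviews before then. A replacement model might therefore be chosen with the results in view. Protocol 4.2's reason for the crossover also does not hold for these two contrasts.

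**Working it through.** **Inputs.** Sequences: Protocol Table 3. Model and code: SAP 6.1 and Appendix 1. N = 12 and within-participant SDs of 0.102, 0.139, 0.206 and 0.269: Protocol 9.5.

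**1. The plan's own precision figures.** Protocol 9.5 gives 90% limits at an estimated ratio of 100%. The formula 100·exp(±t(0.95, df)·SD·√(2/12)·√(χ²(0.80, df)/df)) reproduces them to within 0.05 percentage points at df = 32. The df is not stated and was solved for.

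| Parameter | SD | Computed | Protocol |
|---|---|---|---|
| Nirmatrelvir AUC | 0.102 | 92.56–108.04 | 92.56–108.04 |
| Nirmatrelvir Cmax | 0.139 | 90.00–111.11 | 90.02–111.09 |
| Ritonavir AUC | 0.206 | 85.54–116.90 | 85.54–116.91 |
| Ritonavir Cmax | 0.269 | 81.55–122.62 | 81.52–122.67 |

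(For nirmatrelvir, the sentence under the table attaches the two SDs to the opposite parameters. This does not affect the present point.) The table assumes a contrast variance of 2σ²/12, so it presupposes an estimable contrast.

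**2. Treatment-by-period counts** (12 participants × 5 periods = 60 rows):

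| | Each of Periods 1–3 | Each of Periods 4–5 |
|---|---|---|
| A, B, C | 4 each | 0 |
| D, E | 0 | 6 each |

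In all 60 rows, the Period 4 + Period 5 indicators equal the D + E indicators.

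**3. Rank.** A connected design needs 1 + 5 (sequence) + 4 (period) + 4 (treatment) = 14. The actual rank is 13. D−A, E−A, D−B and all five LS means are not estimable. B−A, C−A and E−D are estimable, each with variance 2σ²/12 = 0.1667σ².

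**4. What the missing dimension means.** Adding d to the D and E effects and subtracting d from Periods 4 and 5 changes no fitted mean. With d = −0.10, 0 and +0.10, true D/A ratios of 1.131, 1.25 and 1.382 give identical expected data.

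**5. Participants and dropout.** With participant effects added, the rank is 19 (60 − 19 = 41 residual df) and D−A and E−A remain non-estimable, since every participant has the same block order. Replacements take the same sequence. In 2000 random dropout patterns D−A was never estimable under the planned model.

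**6. Count.** 4 contrasts × 3 parameters × 2 analytes = 24 primary ratios, of which 2 × 3 × 2 = 12 are lost. Without AUCinf it is 8 of 16.

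**7. Models that give an answer.** The within-block covariates are set out under the fix. Adding their columns to the planned model leaves the rank at 13, so fitted values are identical.

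| Model | Var(D−A), Var(E−A) | df | Bias, drift b per period | Bias, unit step between blocks |
|---|---|---|---|---|
| Within-block period | 0.1667σ² | 41 | 2.5b | 1.0 |
| No period | 0.1667σ² | 44 | 2.5b | 1.0 |
| Linear period | 0.375σ² | 43 | 0 | 1.0 |

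The 2.5 is the difference in mean period, 4.5 − 2. For the linear model, the within-block sum of squares for period is 12 × (2 + 0.5) = 30, so the variance is 1/6 + 2.5²/30 = 0.1667 + 0.2083 = 0.375. That is 2.25 times the variance and 1.5 times the SE.

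**8. 90% CIs at a true ratio of 100%**, exp(±t(0.95, df)·SD·√variance factor), with the estimated SD set equal to the assumed SD:

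| SD | Within-block | Linear period |
|---|---|---|
| 0.102 | half-width 0.0701: 93.2–107.3% | half-width 0.1050: 90.0–111.1% |
| 0.269 | half-width 0.1848: 83.1–120.3% | half-width 0.2769: 75.8–131.9% |

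These omit the 80% coverage factor of Protocol 9.5. With it, at 41 df, the within-block limits are 92.67–107.91 and 81.81–122.23.

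**9. Illustration only.** The documents report no period shift. For assumed log shifts of 0.05 and 0.10, within-block 90% CI coverage (noncentral t, 41 df) is 68% and 24% at SD 0.102, and 87% and 77% at SD 0.269.

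**The case against.** Five points can be made for the plan.

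- **The failure is loud.** A non-estimable contrast yields no number, so the code would not report a wrong ratio. This stands, but it also means the planned analysis does not exist for these contrasts. SAP 6.1 does promise justification for departures, but only after its text on normality and outliers, and it names no replacement. Calling the code an example does not help, because the SAP text specifies the same model.
- **The study only estimates.** There are no hypotheses and no readable decision rule, so no error rate is at risk. That is true, but the estimate and its interval are the primary deliverable.
- **A period shift may be small.** Protocol 4.2 sets a washout of at least 4 days against a nirmatrelvir half-life of about 6 to 13 hours, and participants stay confined throughout. This makes carry-over an unlikely source of a large shift but does not rule out other period effects. The shifts in step 9 are assumptions and carry no weight in the conclusion.
- **Dropping period would do as well.** With complete data it gives D−A and E−A the same variance factor and the same biases, with 44 df instead of 41. Within-block coding is preferable because it keeps B−A and C−A period-adjusted as planned, but it recovers no information about the block shift.
- **Only new sequences cure the problem fully.** This is correct. A 10-sequence Williams set makes every contrast estimable with period in the model, with variance 0.20σ² at 10 participants and 0.10σ² at 20. It is a far larger change than the analytic repair.

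None of these restores the two missing estimates.

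**Conclusion.** The point holds and should be corrected before data release. Under the model in Protocol 9.3.2 and SAP 6.1, D vs A and E vs A are not estimable for any parameter of either analyte: two of four primary objectives and up to 12 of 24 primary ratios. The exploratory D vs B ratio in SAP Section 3 fails in the same way if it uses this model; its analysis text is redacted. B vs A, C vs A and the food effect E vs D stand as planned.

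Non-estimability follows from the sequence table and the model statement alone, with no assumption about variability or period effects. The interval widths for the replacement models do rest on the Protocol 9.5 SDs and complete data from 12 participants. With these sequences, no analysis can separate a step shift between the two blocks of periods from the D/A and E/A effects.

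**What to change.** Before data release, amend SAP 6.1 and Appendix 1, Protocol 9.3.2 and the synopsis as follows.

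1. In the five-treatment model, replace the period factor with three numeric covariates (pb1, pb2, pb3): Period 1 = (1, 0, 0), Period 2 = (0, 1, 0), Period 3 = (−1, −1, 0), Period 4 = (0, 0, 1), Period 5 = (0, 0, −1). The statement becomes `model l&var = seq pb1 pb2 pb3 trt / ddfm=KR`. It serves all four primary contrasts. Keep the D/E-only model for E vs D.
2. State that D/A and E/A then assume no mean shift between Periods 1–3 and Periods 4–5, and that any such shift enters both ratios in full.
3. Prespecify a sensitivity analysis for D/A and E/A with period as a linear numeric covariate, noting that it removes a linear drift but not a step.
4. Qualify the period-effect statement in Protocol 4.2 for these two contrasts.
5. Apply the same change to exploratory D vs B if it uses the same model.

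**Cost:** a few lines of SAS, one sensitivity analysis with a 1.5 times larger SE, and wording. No participants, samples or sequences change. D−A and E−A get the same variance as B−A and C−A only because the no-shift assumption supplies the missing information. A protocol amendment is also needed if the change counts as major under Protocol Section 9.

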6.2. Secondary Endpoints

For the secondary endpoints on the assessment of food effect, same analyses as in the primary endpoints will be used, but with Treatment D as the Reference treatment and Treatment E as the Test treatment.

Analyses and summaries of safety data are described in [Section 6.6](#).

For the taste assessment of the study, the data used in the analysis will be transcribed and rescaled to a score from 0 to 100 from the raw measurements on the questionnaire. The sensory attributes (mouthfeel, bitterness, tongue/mouth burn, throat burn, overall liking) from the taste questionnaires will be listed and descriptively summarized by treatment, and question across participants. Summary statistics (mean and 90% CI) will be calculated for the various questions. Radar plots for each of 4 time points, summarizing all attributes for each treatment will be generated. Boxplots of each attribute will be plotted against the time points.

CCI

CCI	[REDACTED]
[REDACTED]	[REDACTED]

[REDACTED]
[REDACTED]
[REDACTED]

6.4. Subset Analyses

There are no planned subset analyses.

6.5. Baseline and Other Summaries and Analyses

6.5.1. Demographic Summaries

Demographic characteristics (age, gender, ethnicity, race, weight, height and body mass index) will be summarized for enrolled population in accordance with the CaPS.

6.5.2. Study Conduct and Participant Disposition

Participants evaluation groups will show end of study participant disposition. Frequency counts will be supplied for participant discontinuation(s) by treatment. Data will be reported in accordance with the CaPS.

6.5.3. Study Treatment Exposure

Study treatment exposure will be listed.

6.5.4. Concomitant Medications and Nondrug Treatments

All concomitant medication(s) as well as non-drug treatment(s) will be reported in the listings.

6.6. Safety Summaries and Analyses

All safety analyses will be performed on the Safety Analysis Set.

Safety data will be presented in tabular and/or graphical format and summarized descriptively, where appropriate.

6.6.1. Adverse Events

Adverse events will be reported in accordance with the CaPS.

Participant discontinuations due to adverse events will be detailed by treatment. Data will be reported in accordance with the CaPS.

6.6.2. Laboratory Data

Laboratory data will be listed and summarized by treatment in accordance with the CaPS.

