Physical Exam	X	X															
 • PE will be performed by trained medical personnel at the investigator site at Screening or Period 1 Day -1 only (height and weight must be obtained at Screening to obtain BMI for eligibility criteria). A brief PE may be performed at other designated time points at the discretion of the investigator.
Safety laboratory	X	X												X	X		
 • Safety laboratory assessments including urinalysis, hematology, and chemistry will be performed at Screening, Period 1 Day -1, Period 5 Day 4, and early termination/discontinuation if applicable. All the safety laboratory samples must be collected following at least a 4-hour fast. Additional safety laboratory assessments may be performed at any time at the discretion of the investigator.
FSH (postmenopausal women only)	X																
 • For confirmation of postmenopausal (amenorrheic for at least 12 consecutive months) female participants.
Urine drug testing	X	X															
 • Urine drug (mandatory) and alcohol breath test (at discretion of investigator) will be performed at Screening and on Period 1 Day -1. These tests may be performed at any other time at the discretion of the investigator.
Serology: HBsAg, HBsAb, HBcAb, HCVAb, and HIV	X																
 • HBsAb will be tested if HBsAg and/or HBcAb are positive.
Pregnancy test (WOCBP only)	X	X												X	X		

PFIZER CONFIDENTIAL

Table 1. Study Schedule of Assessment

Visit Identifier Abbreviations used in this table may be found in Appendix 10	Screening	Period 1				Period 2, 3 and 4				Period 5				F/U	E/T	Notes			
Days Relative to Day 1	Days -28 to -2	Day -1	1	2	3	4	1	2	3	4	1	2	3	4	28-35 Days				
Contraception check	X	X												X	X	X	
 • The investigator or his/her designee will discuss with the participant the need to use highly effective contraception consistently and correctly according to contraception guidelines (Appendix 4). 		
12-lead ECG (single)	X		X											X		X	
 • Single 12-lead ECG readings will be taken at specified time point. All ECG assessments will be made after at least a 5-minute rest in a supine position and prior to any blood draws or vital sign measurements. • The reading on Period 1 Day 1 will be done predose of Period 1 Day 1. 		

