Vital signs (BP/PR)	X		X				X				X			X		X	
 • Single supine BP and PR will be performed following at least a 5-minute rest in a supine position, at specified time point. BP, and PR assessments will be performed after collection of ECGs and prior to collection of blood draws if scheduled at the same time. Vital signs will be done predose, 2 hours and 6 hours post dose on Day 1 of each treatment period and also on Day 4 of Period 5. 		
COVID-19 questionnaire		X															
 • Check COVID-19 related signs and symptoms as per local procedures. 		
COVID-19 testing		X				X											
 • The testing for COVID-19 pathogen by RT-PCR will be performed as per local procedures. 		
Nirmatrelvir/ ritonavir dosing		X				X				X							
 • Nirmatrelvir/ritonavir will be administered orally after overnight fasting of 10 hours on Day 1 for treatments A, B, C and D and after high fat breakfast for treatment E. There will be at least a 4 day washout between each dose. 		

PFIZER CONFIDENTIAL

Table 1. Study Schedule of Assessment

Visit Identifier Abbreviations used in this table may be found in Appendix 10	Screening	Period 1				Period 2, 3 and 4				Period 5				F/U	E/T	Notes		
Days Relative to Day 1	Days -28 to -2	Day -1	1	2	3	4	1	2	3	4	1	2	3	4	28-35 Days		
 Screening will be performed within 28 days prior to the first dose of nirmatrelvir/ritonavir. Follow-up contact may occur via telephone contact and must occur 28 to 35 days from administration of the final dose of study intervention. 	
Palatability questionnaire Review			X				X										
 Review palatability questionnaire and instructions with participants prior to the first taste assessment to Treatment B, C and D on Day 1 of period 1 or 2. 	
Palatability Questionnaire			X				X				X						
 Each participant will record the sensory attributes at timed intervals of 1 (immediately after dosing), 5, 10 and 20 minutes after swallowing the suspension, using a Taste Assessment Questionnaire (see Appendix 9). PK assessments will take priority if the PK and palatability assessment conflict 	

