3. OBJECTIVES AND ENDPOINTS

Objectives	Endpoints
Primary: 
To estimate the rBA of the nirmatrelvir/ritonavir CCI oral powder mixed with water compared to the nirmatrelvir/ritonavir CCI commercial tablets under fasted conditions.To estimate the rBA of the nirmatrelvir/ritonavir CCI oral powder mixed with infant formula compared to the nirmatrelvir/ritonavir CCI commercial tablets under fasted conditions.To estimate the rBA of the nirmatrelvir/ritonavir CCI oral powder mixed with vanilla pudding compared to the nirmatrelvir/ritonavir CCI commercial tablets under fasted conditions.To estimate the rBA of the nirmatrelvir/ritonavir CCI oral powder mixed with vanilla pudding under fed conditions compared to the nirmatrelvir/ritonavir CCI commercial tablets under fasted conditions.	Primary: 
The test/reference ratios for AUC_{inf} (if data permits), AUC_{last}, and C_{max} of nirmatrelvir and ritonavir.
Secondary: 
To estimate the effect of food on the rBA of the nirmatrelvir/ritonavir CCI oral powder mixed with vanilla pudding.To evaluate the safety and tolerability of nirmatrelvir/ritonavir in healthy participants.To assess the palatability of nirmatrelvir/ritonavir oral powder mixed with water/infant formula/vanilla pudding.	Secondary: 
The test/reference ratios for AUC_{inf} (if data permits), AUC_{last}, and C_{max} of nirmatrelvir and ritonavir.Assessment of TEAEs, clinical laboratory abnormalities, vital signs, PEs, and 12 lead ECGs.Assessment of palatability via questionnaire: mouth feel, bitterness, tongue/mouth burn, throat burn and overall liking.

Objectives	Endpoints
CCI [REDACTED]	[REDACTED]
[REDACTED] [REDACTED]	[REDACTED] [REDACTED]
[REDACTED]	[REDACTED]

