3.5.1. Adverse Events

Any adverse events occurring following start of treatment will be considered as treatment emergent adverse event (TEAE). Events that occur during follow-up within the lag time of up to 28 days after the last of nirmatrelvir/ritonavir dose will be counted as treatment emergent and attributed to the last treatment taken. Events that occur during the washout period (up to 28 days from the last treatment) between study periods will be counted as treatment emergent and attributed to the previous treatment taken. The time period for collecting AEs (“active collection period”) for each participant begins from the time the participant provides informed consent.

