3.5.2. Laboratory Data

Safety laboratory tests will be performed as described in the protocol. To determine if there are any clinically significant laboratory abnormalities, the haematological, clinical chemistry (serum) and urinalysis safety tests will be assessed against the criteria specified in the sponsor reporting standards. The assessment will not take into account whether each participant's baseline test result is within or outside the laboratory reference range for the particular laboratory parameter.

The baseline measurement is the predose measurement on Day -1.

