3.5.3. Vital Signs

Supine blood pressure (BP) and pulse rate (PR) will be measured at times specified in the SoA given in the protocol.

For each period, the baseline measurement is the predose measurement on Day 1.

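### SAP 6.6.2 promises laboratory summaries by treatment, but the only scheduled post-dose sample in completers follows all five treatments

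*SAP*

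**What the plan says.** SAP 6.6.2 sets out the laboratory analysis in one sentence: "Laboratory data will be listed and summarized by treatment in accordance with the CaPS". CaPS is the sponsor's reporting standard and is not part of the documents.

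The sampling schedule is in Protocol section 1.3, Table 1. Safety laboratory tests "will be performed at Screening, Period 1 Day -1, Period 5 Day 4, and early termination/discontinuation if applicable". The investigator may add unscheduled tests at any time. No safety laboratory sample is scheduled after dosing in Periods 1 to 4.

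SAP 3.5.2 fixes one laboratory baseline for the whole study: "The baseline measurement is the predose measurement on Day -1". For vital signs, by contrast, SAP 3.5.3 says: "For each period, the baseline measurement is the predose measurement on Day 1".

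The SAP has an attribution rule for adverse events. Under SAP 3.5.1, events in follow-up after the final dose "will be counted as treatment emergent and attributed to the last treatment taken", and events in a washout go to the preceding treatment. Nothing equivalent is stated for laboratory values.

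Laboratory abnormalities belong to a secondary endpoint. The corresponding objective in Protocol section 3 is "To evaluate the safety and tolerability of nirmatrelvir/ritonavir in healthy participants".

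**The concern.** A by-treatment summary needs at least one post-dose observation that can be tied to each treatment. Here every completer has one scheduled post-dose sample, by which time that participant has received A, B, C, D and E. No attribution rule can make that value specific to one of the five.

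If the table is produced anyway, it invites a comparison between vehicles, and with the reference tablet, that the data cannot support. Under last-treatment attribution, an abnormality still present at Period 5 Day 4 would appear under one of the two vanilla pudding treatments whichever dose preceded its onset. The D and E columns would in fact contrast sequences 4–6 with sequences 1–3. The reference tablet would have no scheduled post-dose result at all.

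An abnormality that resolves before Period 5 Day 4 and is not caught by an unscheduled test would be missed rather than misattributed. That is a property of the sampling schedule, and no change to the table alters it.

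**Working it through.** The documents give no figure to reproduce. The check is a count from the schedule and the randomised sequences.

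**Inputs**
- Scheduled laboratory visits for completers: Screening, Period 1 Day -1, Period 5 Day 4 (Protocol Table 1).
- Six sequences with 2 participants each, 12 in total: ABCDE, BCADE, CABDE, ACBED, BACED, CBAED (Protocol Table 3; SAP Table 2).
- Dose spacing: "There will be at least a 4 day washout between each dose" (Protocol Table 1). I use the 4-day minimum.
- Assumptions: 12 completers and no unscheduled samples.

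**Step 1: scheduled post-dose samples by treatment.** The sample falls in Period 5, which is E in sequences 1–3 (3 × 2 = 6 participants) and D in sequences 4–6 (3 × 2 = 6). A, B and C are never given in Period 5. Twelve participants × 5 periods = 60 treatment-periods, of which 12 contain a scheduled post-dose sample: 12/60 = 20%.

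**Step 2: doses preceding the sample.** In every sequence the set received before Period 5 Day 4 is {A, B, C, D, E}, so all 12 results follow the same five exposures in different orders.

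**Step 3: interval from dose to sample.** With doses 4 days apart, Day 1 of Periods 1 to 5 falls on study days 1, 5, 9, 13 and 17. Period 5 Day 4 is study day 17 + 3 = 20. Interval = 20 − dosing day, giving 19, 15, 11, 7 and 3 days for Periods 1 to 5.

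**Step 4: map the intervals through the sequences.** A, B and C each occupy Periods 1, 2 and 3 in two sequences apiece. D and E each occupy Period 4 in three sequences and Period 5 in the other three.

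| Treatment | Scheduled post-dose samples in its own period | Days from dose to the Period 5 Day 4 sample (participants) |
|---|---|---|
| A | 0 of 12 | 11 (4), 15 (4), 19 (4) |
| B | 0 of 12 | 11 (4), 15 (4), 19 (4) |
| C | 0 of 12 | 11 (4), 15 (4), 19 (4) |
| D | 6 of 12 | 3 (6), 7 (6) |
| E | 6 of 12 | 3 (6), 7 (6) |

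The middle column is also what a by-treatment table would contain under last-treatment attribution. Longer dose spacing would lengthen every interval except the 3 days.

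**The case against.** The strongest reply is that the harm depends on a convention nobody outside the sponsor can see. CaPS may already present a single end-of-study value as a pooled row, in which case no misleading D and E columns would appear. This stands as a limit on certainty: the 6/6 split is conditional. It does not rescue the sentence in SAP 6.6.2, because no reporting standard can supply scheduled samples after A, B or C.

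Other text softens the effect. Clinically significant laboratory changes are recorded as adverse events (Protocol 8.3.4 and Appendix 3) and so fall under the SAP 3.5.1 attribution rule. Protocol 9.3.3 has abnormalities of potential concern described, and both it and SAP 6.6 qualify summaries by appropriateness. This reduces the chance that an important result is lost. However, the adverse-event rule still assigns by recency, and the general qualifier is followed in SAP 6.6.2 by a specific commitment to summarise by treatment.

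The single baseline matters less than it may seem. SAP 3.5.2 assesses abnormalities without regard to whether the baseline value was inside the reference range. Nor does the contrast with vital signs show a better planned analysis, since SAP 6.6.3 plans no vital-sign table and only holds the data for request. Both points are fair. The case rests on the absence of post-dose samples, not on the baseline.

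Finally, Protocol 4.2 gives a nirmatrelvir half-life of about 6 to 13 hours with ritonavir. Seven days is 168 hours, and 168/13 ≈ 12.9 half-lives, so nirmatrelvir from earlier periods should be essentially gone and reading the sample as following the last dose is not arbitrary. But a laboratory change can outlast the drug, the public text gives no ritonavir half-life, and this argument does nothing for A, B or C.

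**Conclusion.** The concern holds. The by-treatment laboratory summary committed to in SAP 6.6.2 cannot be delivered from the scheduled samples of completers: 0 of 12 participants have a scheduled post-dose result in the period of A, B or C, and the 6 each in the periods of D and E follow all five treatments. The sampling facts come directly from the documents. The allocation to D and E columns assumes last-treatment attribution, and the counts assume 12 completers. Early-termination or unscheduled tests could add isolated results after fewer doses, but they would not make a by-treatment table.

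This should be corrected but is not critical. The table is descriptive, no hypothesis is tested, the PK estimates are untouched and individual results remain in the listing. The safety objective concerns nirmatrelvir/ritonavir as a whole, so no stated objective is lost by dropping the split.

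**What to change.** Reword SAP 6.6.2 as follows:

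- Summarise scheduled laboratory data for all participants combined, comparing the Day -1 baseline with Period 5 Day 4 or early termination.
- List abnormalities with treatment sequence and the timing of the sample relative to dosing.
- Link a result to the most recent treatment only where it is an unscheduled within-period or early-termination sample, and do so in the listing.

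Stating an attribution rule while keeping the by-treatment table would make the output reproducible. It would still leave A, B and C without scheduled results, and D and E confounded with sequence, so the overall summary is preferable.

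The cost is SAP wording and one simpler table. No extra blood samples and no protocol amendment are needed.
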